2.2.2 Secondary Endpoints

Tolerability - 75% of patients will be able to tolerate trial medication, in at least half dose, up to one year after randomisation (i.e. less than 25% will stop trial medication completely through inability to tolerate the drugs).

Safety - symptoms of systemic or intracranial bleeding, recurrent cerebral and systemic vascular events, and vascular and non-vascular causes of death will be collected. The absolute risk of death, including fatal haemorrhage, will not differ significantly (ie fall outside the upper 95% CI) from 2% per year on trial drugs versus no trial drugs, when given in addition to guideline drugs; and will not increase bleeding or ischaemic SVD lesions significantly (at the p<0.01 level) on MRI.

Efficacy – individual event-rate data (stroke, TIA, myocardial ischaemia, cognitive impairment and dementia, will be collected. The *combined rate* of recurrent stroke, MI, death, cognitive impairment and dependency will be 40-50% at one year after enrolment in order to detect modest but clinically-important reductions in poor outcomes.

Health Economics – data to assess health economic impact will be gathered.

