The doses will be escalated until participants are on their full dose by 1 month. If a patient encounters intolerable side effects at full dose, then they will be able to remain on the highest dose regime that they can tolerate and this dose will be recorded. The total duration of the trial drug administration will be 1 year.

Note that no maximum time since the index lacunar ischaemic stroke will be set – patients will be eligible for the trial for several years after their lacunar stroke at the discretion of the local medical staff, as long as the index stroke was compatible with lacunar ischaemic stroke and competing pathologies as a cause of the stroke were excluded using contemporaneous MR imaging, or CT, as above. That is, that the index stroke was not a non-lacunar stroke, that it was ischaemic and not haemorrhagic, and that it was not a non-stroke based on clinical and MR imaging, or CT, acquired at the time of the stroke.

Note also that no minimum cut off cognitive score is set. The Montreal Cognitive Assessment (MOCA) will be collected at baseline but will not be an inclusion/exclusion criterion. The important point is that the patient has capacity to consent, in the opinion of the randomising doctor.

[figure not shown]
Throughout the trial, patients will continue to take their normal prescribed medication which will include stroke secondary prevention prescribed since their event as per national guidelines/usual post-stroke care in participating centres.

Four hundred patients will be recruited from UK stroke research network centres. The most active of these sites see 10-15 patients per month with suspected lacunar stroke, of whom 25-33% would be eligible. Some interested sites have indicated that they could randomise 1-2 per month. Patients will be recruited from hospital-based stroke services, including patients who have participated in previous completed studies and indicated that they would like to be informed of future stroke studies.

On entry to the study, participants will be assessed by the study researcher, including presenting history, past medical history, medication history, neurological examination, check of brain MR or CT scan, blood pressure measurement and cognitive testing. They will then be randomised.

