4.3 EXCLUSION CRITERIA

4.3.1 General exclusion criteria

- Other significant active neurological illness present since suffering stroke (e.g. recurrent seizures, multiple sclerosis, brain tumour). Well-controlled epilepsy present prior to the stroke, a single seizure at onset of the stroke or provoked seizure is not an exclusion.
- Requiring assistance with activities of daily living (Modified Rankin ≥ 3)
- Has been diagnosed as having dementia on formal clinical assessment
- Diagnosis of hypotension, defined as sitting systolic blood pressure less than 100mmHg
- Unable to swallow tablets
- Planned surgery during the trial period including carotid endarterectomy. Note prior and apparently successful carotid endarterectomy (or other surgery) is not an exclusion criterion and patients who would otherwise be eligible but require endarterectomy first may be randomised after recovery from successful endarterectomy.
- Other concurrent life threatening illness
- Unlikely to be available for follow-up (e.g. moving outside or visitor to the area)
- History of drug overdose or attempted suicide or significant active mental illness
- Pregnant or breastfeeding women, women of childbearing age not taking contraception. Acceptable contraception in women of childbearing age is a “highly effective” contraceptive measure as defined by the Clinical Trials Facilitation Group (http://www.hma.eu/fileadmin/dateien/Human_Medicines/01-About_HMA/Working_Groups/CTFG/2014_09_HMA_CTFG_Contraception.pdf) and includes combined (oestrogen and progesterone containing) or progesterone-only contraception associated with inhibition of ovulation, or intrauterine device or bilateral tubal occlusion. Contraception must be continued for up to 30 days after the end of the IMP dosing schedule.
- Renal impairment (creatinine clearance <25 ml/min)
- Hepatic impairment
- Current enrolment in another Clinical Trial of Investigational Medicinal Product (CTIMP); still in extended follow-up beyond the CTIMP primary outcome and no longer taking that trial's IMP is not an exclusion to enrolment in LACI-2.
- Unable to tolerate MRI or contraindication to MRI (Claustrophobia, Pacemaker)

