9 STATISTICS AND DATA ANALYSIS

9.1 SAMPLE SIZE CALCULATION

There are few data on which to base sample size. There is little experience with cilostazol in Europe or North America, and little experience with ISMN in this group of patients in the UK (or in any patients with stroke). We have been guided by colleagues in Japan where cilostazol is in common use and there is experience with it in stroke. The main purposes of the trial are to assess tolerability and safety.

Table 6 Annual absolute risks (%) of outcome events after lacunar stroke

Vascular death	Non-vasc death	Non-fatal isch stroke or TIA	Non-fatal ICH	MI	MACE	Dependent (mRS 3-5)	Any cogn impt.	Dementia
1.8	0.5	2.5	0.5	0.6	3	15	30	15

We calculated mean annual event rates (Table 6) from trials (SPS3,³³ lacunar patients in ENOS⁵⁰ IST-3,⁶³ of cilostazol, Figure 1) and observational data (LADIS;⁶⁴ our^{4, 65} and other⁶⁶

studies). We expect deaths including vascular deaths of median 2.0% p.a., with 4% being the upper 95% CI of 2% in 400 patients.³³ LACI-2 therefore has a sample size of 400.

For a main Phase III trial, recurrent stroke 2.5%pa, MI 0.6%pa and vascular death 1.8%pa,^{4, 33} (MACE) are infrequent; new cognitive impairment c16% at one year,^{6, 66} dependency 15%, are frequent and important to patients, justifying their inclusion in a composite primary outcome. However, these event rates are imprecise with wide ranges; more precise estimates are needed. We estimate main Phase III trial sample size at 1100 (Table 7), assuming 80% power, alpha 5%, 10% loss to follow-up, composite event rate (45%) and conservative estimate of cilostazol effect (20% RRR is the lower 95% CI of effect, Figure 1). A primary outcome including MRI SVD progression (A, below) was considered but at least 15% of patients miss repeat MRI, sample sizes were similar (or larger, due to variance in WMH change⁶⁵ short term), the cost is much higher and the WMH intermediary measure is less relevant to patients.

Table 7. Sample size for composite outcome in main trial, estimated event rates.

Composite model	A	B	Ci	Cii	D
Composite outcome for Phase III includes:	MACE, dementia, non-vasc death, new MR signs	MACE, dementia, death	MACE, cog↓, dependency↓, death		MACE, cog imp, depend, all death
1-beta (power)	80%	80%	80%	80%	80%
Event rate, control, pa	50%	10%	30%	30%	45%
Relative risk reduction	20%	20%	20%	30%	20%
Event rate, active, pa	40%	8%	24%	21%	36%
Total sample size	950	6626	1784	778	976

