- Death, including fatal haemorrhage, aiming for less than outside the upper 95% CI of 2% per year.
- The *combined rate* of recurrent stroke, MI, death, cognitive impairment and dependency, aiming for 40-50% at one year after enrolment.

Comparison of rates of events between the treatment groups: cilostazol vs no cilostazol, ISMN vs no ISMN, and cilostazol and ISMN vs neither, for:

- Systemic or intracranial bleeding, recurrent cerebral and systemic vascular events, and vascular and non-vascular causes of death.
- Death, all cause.
- New ischaemic or haemorrhagic stroke lesion or increase in SVD lesions on MRI.
- Composite of: recurrent clinically-evident stroke, MI, death, cognitive impairment (including dementia) and dependency.
- Individual event: stroke (clinically-evident or imaging-detected ischaemic or haemorrhagic stroke to be reported separately), TIA, myocardial ischaemia, cognitive impairment and dementia.
- New infarcts and haemorrhages, absolute and change in WMH, microhaemorrhages, lacunes, atrophy imaging variables from central read of baseline imaging and one year MRI
- The comparisons of combined cilostazol and ISMN versus neither, whilst being very underpowered statistically, are presented since these may be the two groups studied in the planned follow-on trial.

Central tendency, comparisons and regressions will be analysed as follows (**Table D**).

Table D. Descriptive and analytical statistics

	Binary	Nominal	Ordinal	Continuous
Central tendency and distribution	N (%)	N (%)	Median [interquartile range]	Mean (standard deviation)
Comparisons	Chi-square (2x2)	Chi-square (2x2, or rxc)	Mann-Whitney U or Kruskal-Wallis	t-test (pooled) or 1-way ANOVA
Regression	Binary logistic regression (BLR)	-	Ordinal logistic regression (OLR)	Multiple linear regression (MLR)

27b Covariate adjustment: Analyses will be adjusted for minimisation covariates:

- Age, sex, stroke severity (NIHSS), dependency resulting from the stroke, systolic blood pressure, smoking status, time after stroke, years of education.

Covariate adjustment with continuous variables (age, NIHSS, SBP, time after stroke, years of education) will use original, not dichotomised, data.

27c Assumption checking: The assumption of proportionality will be tested using the likelihood test.

27d Alternative methods: If the data fail the assumption of proportionality (tested using the likelihood test), we will use alternative methods such as multiple logistic regression.

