We will categorise cognition into 7- and 4-level ordinal scales based on DSM-V²² categorisation (Table E).²³ We will calculate scores for cognitive domains using sub-scores of MoCA (or TICS if missing) although we recognise that these global cognitive assessments have some test items that map to a more than one domain, e.g. the

clock drawing test in the MoCA includes aspects of attention, executive function and visual-perceptual function.

- Learning and memory: orientation in place (from MoCA), delayed recall of five word (MoCA), and recall and delayed recall of ten words (TICS)
- Language: using comprehension, semantic and recent memory (from MoCA; similar elements in TICS-M)
- Perceptual-motor function: Cube copy and clock drawing from MoCA
- Executive function: Trail making tests A & B, verbal fluency test (VFT-phonemic)-F (from MoCA); verbal fluency test (VFT-semantic)-animals; clock drawing test (from MoCA); digits forward (from MoCA); digits backward (from MoCA)
- Complex attention: using serial sevens subtraction (MoCA), letter tapping (MoCA)
- Social cognition is not classically assessed in cognitive screening tools and there are no agreed generic short form assessments for social cognition. Aspects of social cognition will be assessed through informant data and NPI-Q although these are not part of the core outcome set.

Table E. Categorisation of cognition based on DSM V with operationalisation (adapted summary from ²³).

	Seven-level categorisation and operationalisation	Four-level categorisation and operationalisation
Normal cognition	No evidence of cognitive impairment (T-MoCA:20-22 AND TICS-m: 25-39)	No evidence of cognitive impairment (T-MoCA:20-22 AND TICS-m: 25-39)
Minor Neurocognitive disorder (mild cognitive impairment)	Single domain Scores are reduced by > 1 point in only one cognitive domain of T-MoCA	Evidence of cognitive impairment (T-MoCA: 15-19 OR TICS-m: 17-24) AND
	Multi-domain Scores are reduced by > 1 point in more than one cognitive domain of T-MoCA	No evidence of functional impairment (mRS <2 OR no change in mRS if pre-stroke mRS >1)
Major neurocognitive disorder	Mild cognitive impairments (T-MoCA 15-19 OR TICS-m 17-23) AND Mild dysfunction (mRS <3)	Persisting cognitive impairment (T-MoCA score <19 OR TICS-m<24 on more than one follow-up) AND Functional impairment (mRS ≥2 or IQCODE >3.6 at final follow-up)

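### The composite and its 40-50% criterion count cognitive impairment at one year without requiring it to be new, although patients already impaired may enrol

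*SAP*

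**What the plan says.** **The outcome.** SAP 27a lists for comparison between arms a "Composite of: recurrent clinically-evident stroke, MI, death, cognitive impairment (including dementia) and dependency". The associated rate criterion, in SAP 27a's tabulations, is "recurrent stroke, MI, death, cognitive impairment and dependency, aiming for 40-50% at one year after enrolment". Protocol 2.2.2 has the same five components: "recurrent stroke, MI, death, cognitive impairment and dependency will be 40-50% at one year after enrolment". Protocol 2.2.2 and SAP 26a give the purpose of the target, which is to make a modest but worthwhile reduction detectable in Phase III.

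**Entry.** Protocol section 3 states: "Note also that no minimum cut off cognitive score is set". It says of the baseline MoCA that it "will be collected at baseline but will not be an inclusion/exclusion criterion". The one cognitive exclusion in Protocol 4.3.1 is "Has been diagnosed as having dementia on formal clinical assessment". Section 3 sets no upper limit on time since the index stroke. Dependency is handled differently: Protocol 4.2 requires mRS of 2 or less, so mRS above 2 at one year is new.

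**Measurement.** The baseline visit has MoCA and Trails B. T-MoCA and TICS are first scheduled at six months (Protocol Table 5, SAP Table C). The only operational cut-offs are in SAP Table E (section 29), for example "Evidence of cognitive impairment (T-MoCA: 15-19 OR TICS-m: 17-24" in the four-level scale.

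**Planning figures.** Protocol 9.1 justifies the component by "new cognitive impairment c16% at one year", while Protocol Table 6 carries any cognitive impairment at 30%. Protocol Table 7 separates a composite built on decline (model Ci, 30%) from one built on impairment (model D, 45%).

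**Adjustment.** SAP 27b adjusts for the minimisation variables, which do not include baseline cognition. SAP Section 7 names cognitive ability at randomisation as a measured confounder of the composite.

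**The concern.** Death, stroke, MI and dependency can enter the composite only if they arise after randomisation. Cognitive impairment is the exception. A patient who enrols with a low score and is unchanged a year later can be counted as an event.

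Two uses of the result are affected. First, the 40-50% criterion is read as an absolute rate and taken as evidence that Phase III would have enough events to work on. If part of the rate was present before treatment, that inference fails to the same extent. Secondly, in the arm comparisons stable cases add equal numbers of events to both sides and pull the relative effect toward the null. A Phase III size built on 45% with a full 20% reduction would then be too small.

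**Working it through.** **1. Reproduce the plan's figure.** Inputs from Protocol 9.1 and Table 7, model D: 45% v 36%, 80% power, alpha 5% (taken as two-sided), 1:1 allocation, Fleiss correction. With p̄ the mean of the two rates and d their difference, the size per arm is

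n = [1.960·√(2p̄(1−p̄)) + 0.842·√(p₁(1−p₁)+p₂(1−p₂))]² / d²

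and the corrected size is n′ = (n/4)·[1 + √(1 + 4/(n·d))]².

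With p̄ = 0.405 and d = 0.09, n is about 466 and n′ = 488, a total of **976**, as stated. The same formula returns the stated 1784 for model Ci (30% v 24%), 778 for Cii and 6626 for B.

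**2. Which cognitive rate does the 40-50% target need?** Other components from Protocol Table 6: ischaemic stroke or TIA 2.5%, ICH 0.5%, MI 0.6%, death 1.8 + 0.5 = 2.3%, dependency 15%. (The first figure includes TIA, which the five-component composite does not.)

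- Any impairment, 30%, independent components: 1 − 0.70×0.85×0.975×0.995×0.994×0.977 = **43.9%**. Plain sum: 50.9%.
- New impairment, 16%, independent components: 1 − 0.84×0.85×0.975×0.995×0.994×0.977 = **32.7%**. Plain sum: 36.9%.

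The plain sum is the largest value the combined rate can take whatever the overlap. With these inputs the new-impairment version therefore stays below 40%, while the any-impairment version falls inside the target under independence.

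**3. Dilution.** Let s points of a 45% control rate be impairment present at entry, with no other component event, and unaffected by treatment. If the 20% reduction acts on the rest, the active rate is 45 − 0.20×(45 − s), and the overall relative reduction is 0.20×(45 − s)/45. The documents give no value for s, so it is varied. Power is at 488 per arm without continuity correction; required totals use the corrected formula in step 1.

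| s (points, assumed) | Active rate | Overall relative reduction | Power at 976 | Total for 80% power |
|---|---|---|---|---|
| 0 | 36% | 20.0% | 82% | 976 |
| 5 | 37% | 17.8% | 72% | 1234 |
| 10 | 38% | 15.6% | 60% | 1610 |
| 20 | 40% | 11.1% | 35% | 3148 |

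**4. Cross-check without s.** The plan's own decline composite, model Ci at 30% v 24%, needs 1784, which is 1784/976 = 1.83 times model D. With 976 patients its power is about 56%.

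**The case against.** Several objections carry weight.

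- **No entry prevalence is given.** A reader might subtract 16% from 30% and conclude that 14 points, nearly half of the expected cognitive events, are prevalent. The documents do not support that. Protocol Table 6 is labelled as annual risks. Its word *any* stands beside a separate dementia column and may mean any severity. The 30% and the 16% may rest on different sources, and neither is shown to apply to patients with mRS of 2 or less and no diagnosed dementia. Hence the range for s.
- **Treatment might improve existing impairment.** A reader might infer that neither drug could alter these cases. The Protocol's rationale includes possible myelin repair and better vessel function (1.1, 1.2), so zero effect is an assumption of step 3, not a fact.
- **SAP Table E is not said to define the binary component.** It sits under additional analyses, and its seven-level minor category speaks of reduced scores, which could mean change. However, T-MoCA has no baseline value from which to measure change. What stands is that the component is left undefined as to new or existing impairment.
- **The composite varies between places.** SAP 26a adds new stroke lesions on scanning, and SAP Table 2 includes TIA. The figures above concern the five-component version; the effect on the 26a version is not established.
- **The stakes within this trial are limited.** The primary endpoint is recruitment and retention, and the 400 was not sized on this composite. The Protocol calls its rates imprecise, shows decline and impairment models side by side, and the SAP reports component rates and baseline MoCA.

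These points limit the size and seriousness of the concern. They do not answer the central gap: the criterion, as worded, cannot separate impairment that patients brought with them from impairment that arose in the trial.

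**Conclusion.** The point holds as a definitional gap that should be fixed, with moderate consequences. The 40-50% rate can be met partly by impairment present at entry, and meeting it does not by itself show that Phase III could detect a modest reduction. On the plan's component rates under independence, the choice between any and new impairment moves the combined rate from about 44% to about 33%, across the lower limit of the target.

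The Phase III consequence depends on a share that the documents do not give. For an assumed 5 to 20 points of prevalent-only cases with no treatment effect, the overall relative reduction is about 18% to 11%, power at 976 is about 72% to 35%, and 80% power needs about 1234 to 3148 patients. The plan's own decline model, at 1784, lies within that span.

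A reader might also infer that the arm comparisons are biased. They are not: randomisation should balance impairment at entry, so the effect is dilution and lost precision. The feasibility endpoint and the target of 400 are untouched.

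**What to change.** 1. In SAP 26a and 27a, state the rule for the binary cognitive component: which instrument, which cut-off, and whether it must be new.
2. In SAP Table 2, report the combined rate twice: with any impairment, and with new or worsened impairment. Class entry status from the baseline MoCA and use the same instrument family at 12 months, through the items MoCA and T-MoCA share, if item-level data are held. Otherwise report the rate with and without participants at MoCA 24 or below at entry, a row already planned in SAP Table 1.
3. Do not let TICS-m alone make a case new. It has no baseline value, so an unchanged patient could be labelled as a new event.
4. Base the Phase III event-rate judgement on the new or worsened rate.
5. Add baseline MoCA to the SAP 27b covariates for the composite and cognitive outcomes.

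**Cost.** SAP wording, one derived variable and one covariate, from an assessment already scheduled. The headline rate will be lower and may miss 40-50%. In-person and telephone scores differ in mode, so some apparent change will be artefact. Under the complete-data rule in SAP 20, anyone without a baseline MoCA would drop out of the adjusted models.

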9.2 PROPOSED ANALYSES

We will compare cilostazol v no cilostazol, ISMN v no ISMN, cilostazol and ISMN v neither. The proportion completing to target dose and any adverse events will be assessed using odds ratios. The LACI-2 will focus on numbers recruited, retained, tolerance and safety outcomes, blinded for TSC and unblinded intention to treat (ITT) for DMC. Safety analysis will use: Kaplan-Meier and Cox proportional regression for analysis of time-to-event outcomes of death; binary logistic regression for SAEs, recurrent stroke, MI, and in those completing 12 month MRI, the amount of microbleeds, siderosis, new infarcts, WMH burden; all adjusted for minimisation variables to maximise power.⁶⁷ We will collect data for future health economics analysis (EQ-5D-5L, EQ-VAS).

A secondary ITT analysis will be performed using logistic regression adjusted for minimisation variables of cilostazol+/-ISMN versus control on efficacy and safety outcomes, with secondary tests of subgroup interactions. Ordinal logistic regression will be used for ordinal categorical outcomes (e.g. mRS) to increase power.⁶⁸

A Statistical Analysis Plan (SAP) will be published prior to database lock and will describe analysis procedures and procedures for missing, unused or spurious data, and definitions of populations analysed.

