- Recruitment of sufficient patients, i.e. 400 patients in 24 months in the UK (and taking account of interruption due to COVID-19).
- >95% of randomised patients are retained for follow-up at one year.

Secondary outcomes - participant

Tolerability: 75% of patients will be able to tolerate trial medication, in at least half dose, up to one year after randomisation (i.e. less than 25% will stop trial medication completely through inability to tolerate the drugs).

Safety

- Symptoms of systemic or intracranial bleeding.
- The absolute risk of death, including fatal haemorrhage, does not differ significantly, i.e. fall outside the upper 95% CI of 2% per year on trial drugs versus no trial drugs, when given in addition to guideline stroke prevention drugs.
- There are no new ischaemic or haemorrhagic brain lesions or increase in SVD lesions on one year MRI significantly (at the p<0.01 level).

Efficacy

- Individual event-rates for stroke, TIA, myocardial ischaemia, cognitive impairment and dementia.
- The *combined rate* of recurrent stroke, MI, death, mild cognitive impairment (including dementia), dependency and new stroke lesions on scanning at 1 year will be 40-50% at one year after enrolment in order to allow detection of a modest but clinically-important reduction in poor outcomes in a phase III trial.
- Health economic measures include the health utility score (EQ-5D-5L) and the visual analogue score (EQVAS) at 12 months.

26b Units: Units will be shown in tables.

26c Calculations/transformations: Quality of life using UK weightings.

Brain frailty

Based on neuroimaging:

- Brain frailty = Atrophy + WML + Previous stroke lesion ⁷

- SVD score for CT = WML, lacunes; for MRI includes WMH, lacunes, PVS and microbleeds ¹⁵

Montreal cognitive assessment-modified (MoCA-m) trails

Since Trails A and B are performed, the MoCA trail is not collected but rather estimated from the Trails B score:

- If Trails B score <12 then MoCA trail = 0
- If Trails B score >=12 then MoCA trail = 1

27 Analysis methods

27a Methods

Primary endpoint

- Tabulation and graphical presentation of participant recruitment aiming for 400 participants in 24 months.
- Tabulation of retention of participants at one year aiming for >95%.

Analyses of secondary outcomes

Tabulations of:

- Tolerability to trial medications aiming for 75% of patients taking at least half dose for up to one year after randomisation.

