Heart rate (bpm)	XX (X)	XX (X)	MLR	XX (X)	XX (X)	MLR	XX (X)	XX (X)	MLR
mRS	XX (X)	XX (X)	OLR	XX (X)	XX (X)	OLR	XX (X)	XX (X)	OLR
Disposition	XX (X)	XX (X)	OLR	XX (X)	XX (X)	OLR	XX (X)	XX (X)	OLR
ZDS	XX (X)	XX (X)	MLR	XX (X)	XX (X)	MLR	XX (X)	XX (X)	MLR
Clinical depression	XX (X)	XX (X)	BLR	XX (X)	XX (X)	BLR	XX (X)	XX (X)	BLR
EQ-5D-5L, as HU	XX (X)	XX (X)	MLR	XX (X)	XX (X)	MLR	XX (X)	XX (X)	MLR
EQ-VAS	XX (X)	XX (X)	MLR	XX (X)	XX (X)	MLR	XX (X)	XX (X)	MLR
SIS	XX (X)	XX (X)	MLR	XX (X)	XX (X)	MLR	XX (X)	XX (X)	MLR
Global	XX (X)	XX (X)	WLT	XX (X)	XX (X)	WLT	XX (X)	XX (X)	WLT

BP: blood pressure; MoCA: Montreal cognitive assessment-modified; mRS: modified Rankin Scale; SIS: stroke impact scale; TICS-m: Telephone interview cognitive status- modified; ZDS: Zung depression scale
 Global: Recurrent ordinal stroke,¹⁷ ordinal MI, cognition (MoCA), dependency (mRS), stroke impact scale, quality of life (EQ-5D).

Table 4. Adherence to medication with at least half dose or more by randomised group: isosorbide mononitrate (ISMN), cilostazol (Cil) and both together.

Week	ISMN	No ISMN	p	Cilostazol	No cilostazol	p	ISMN +Cil	ISMN alone	Cil only	Neither	p
1-2	XX (X)	XX (X)	Chi-sq	XX (X)	XX (X)	Chi-sq	XX (X)	XX (X)	XX (X)	XX (X)	Chi-sq
3-4	XX (X)	XX (X)	Chi-sq	XX (X)	XX (X)	Chi-sq	XX (X)	XX (X)	XX (X)	XX (X)	Chi-sq
26	XX (X)	XX (X)	Chi-sq	XX (X)	XX (X)	Chi-sq	XX (X)	XX (X)	XX (X)	XX (X)	Chi-sq
52	XX (X)	XX (X)	Chi-sq	XX (X)	XX (X)	Chi-sq	XX (X)	XX (X)	XX (X)	XX (X)	Chi-sq

A more detailed table by strata of drug adherence (i.e. 25%, 50%, 75% and 100% adherence) will also be prepared.

Table 5. Adjudicated baseline imaging characteristics by randomised group: isosorbide mononitrate (ISMN), cilostazol (Cil) and both together.

Data are number (%), median [IQR], or mean (standard deviation).

	N	All	ISMN	No ISMN	Cil	No Cil	ISMN + Cil	ISMN only	Cil only	None
Patients randomised	XX	XX	XX	XX	XX	XX	XX	XX	XX	XX
Scan										
Scan type(%)										
CT	XX	XX (X)	XX (X)	XX (X)	XX (X)	XX (X)	XX (X)	XX (X)	XX (X)	XX (X)
Time to scan (days)	XX	XX (X)	XX (X)	XX (X)	XX (X)	XX (X)	XX (X)	XX (X)	XX (X)	XX (X)
MR	XX	XX (X)	XX (X)	XX (X)	XX (X)	XX (X)	XX (X)	XX (X)	XX (X)	XX (X)
Time to scan (days)	XX	XX (X)	XX (X)	XX (X)	XX (X)	XX (X)	XX (X)	XX (X)	XX (X)	XX (X)
Scan quality (%)										
Good	XX	XX (X)	XX (X)	XX (X)	XX (X)	XX (X)	XX (X)	XX (X)	XX (X)	XX (X)
Moderate	XX	XX (X)	XX (X)	XX (X)	XX (X)	XX (X)	XX (X)	XX (X)	XX (X)	XX (X)

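### The one-year MRI models omit the baseline reading of the same feature: a large precision loss in the absolute rows of SAP Table 9, a small one in the change rows

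*SAP*

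**What the plan says.** The outcome bullet in SAP 27a reads "New infarcts and haemorrhages, absolute and change in WMH, microhaemorrhages, lacunes, atrophy imaging variables", and goes on to take these from the central readings of both the baseline and the one-year scans. Table 9 turns this into three kinds of row, analysed by binary or ordinal logistic regression:

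- **New lesions:** evidence of new ischaemic or haemorrhagic stroke.
- **Absolute status at one year:** microhaemorrhage presence and number, SVD score, atrophy, WMH presence, Fazekas scores, white-matter lucency, lacune number, old infarct types and probable old haemorrhage.
- **Change from baseline:** microhaemorrhage number, SVD score, atrophy, Fazekas scores, WMH overall and by region, and lacune number.

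SAP 27b sets the covariates: "Analyses will be adjusted for minimisation covariates", namely "Age, sex, stroke severity (NIHSS), dependency resulting from the stroke, systolic blood pressure, smoking status, time after stroke, years of education". Protocol 9.2 gives the same rule for the 12-month MRI outcomes: "all adjusted for minimisation variables to maximise power". Neither adds a baseline imaging value. The readings exist, under "Table 5. Adjudicated baseline imaging characteristics by randomised group", and SAP Section 7 counts SVD lesion severity among the measured confounders of the composite outcome.

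The MRI safety criterion in SAP 26a is "There are no new ischaemic or haemorrhagic brain lesions or increase in SVD lesions on one year MRI significantly", with the threshold at p<0.01. No text says which Table 9 rows decide it.

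**The concern.** Microbleeds, lacunes, old infarcts and white-matter disease largely persist. For an absolute one-year row, the same feature on the baseline scan is therefore likely to be the strongest available predictor. Leaving it out has two effects: variation between patients that was there before treatment stays in the error term, and any chance imbalance between arms at baseline stays in the estimate.

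The direction matters because of how the criterion is worded. It is satisfied when no increase is significant at p<0.01, so a less precise model makes a finding of safety easier to reach.

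Subtracting baseline, as the change rows do, removes most of the problem but is not fully efficient. White-matter lucency, the old non-lacunar infarct types and probable old haemorrhage have no change row of their own. Diastolic BP in SAP Table 3 has a similar gap: it is recorded at baseline (Table 1) and compared at 12 months without the baseline value in the model.

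**Working it through.** **The plan's own figure.** No power or detectable difference is given for any MRI outcome. The only basis for N=400 is a 2% death rate with an upper 95% limit of 4%. That reproduces (8/400 has an exact upper limit of 3.90%) but does not bear on imaging.

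**Inputs from the documents.** 363 randomised (SAP Table 2); at least 15% miss repeat MRI (protocol 9.1); 1:1 allocation for each drug (protocol 5.5.1); threshold p<0.01 (SAP 26a), taken as two-sided. Scans: 363 × 0.85 = 308.55, so about 154 per side. This is an upper figure, since the partial factorial design leaves some patients out of each comparison.

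**Assumed.** The documents give no correlation rho between baseline and one-year readings. The range shown is 0.5 to 0.95.

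**Scores.** With equal SDs, variances relative to a follow-up-only analysis are:

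- follow-up only: 1
- change: 2(1−rho)
- baseline-adjusted: 1−rho²

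So follow-up-only against adjusted is 1/(1−rho²), and change against adjusted is 2/(1+rho). The smallest difference detectable with 80% power is (2.576+0.842) × √(variance × 2/154), in SD units; with variance 1 this is 0.389.

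| rho | Variance, absolute ÷ adjusted | Variance, change ÷ adjusted | Detectable: absolute / change / adjusted | Power of absolute / change where adjusted has 80% |
|---|---|---|---|---|
| 0.5 | 1.33 | 1.33 | 0.389 / 0.389 / 0.337 | 65% / 65% |
| 0.7 | 1.96 | 1.18 | 0.389 / 0.302 / 0.278 | 45% / 72% |
| 0.8 | 2.78 | 1.11 | 0.389 / 0.246 / 0.234 | 30% / 75% |
| 0.9 | 5.26 | 1.05 | 0.389 / 0.174 / 0.170 | 14% / 77% |
| 0.95 | 10.3 | 1.03 | 0.389 / 0.123 / 0.122 | 7% / 79% |

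A simulation of a four-level ordinal feature (4,000 trials per setting, linear score models, latent shift 0.3 SD, p<0.01) agrees. Power for absolute / change / adjusted was 45/40/55% at rho 0.5, 44/60/71% at 0.7, 46/76/82% at 0.8 and 44/92/95% at 0.9. Type I error was near 1% for all three.

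**Presence against new lesion.** Assume 20% to 50% have the lesion at baseline, it persists, and new lesions rise from 10% to 20%. At 20% prevalence, presence at one year is 0.2 + 0.8×0.1 = 28% against 0.2 + 0.8×0.2 = 36%. Power at p<0.01 is 14%, falling to 5% at 50% prevalence. A new-lesion row (10% v 20%) has 45%.

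**Microbleed example with the change analysis included.** Assume 309 scans, 25% prevalence at baseline, 97% persistence, and new microbleeds in 5% v 12% of those without any; 1,500 trials. Change is follow-up minus baseline presence, tested by Mann-Whitney.

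| New microbleeds | Threshold | Presence, unadjusted | Presence, baseline-adjusted | Change |
|---|---|---|---|---|
| 5% v 12% | p<0.05 | 17% | 44% | 44% |
| 5% v 12% | p<0.01 | 6% | 17% | 21% |
| 5% v 15% | p<0.05 | 30% | 63% | 66% |
| 5% v 15% | p<0.01 | 12% | 37% | 42% |

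Repeat runs move these by a few points. Adjustment more than doubles the power of the presence row but does no better than change. Table 9's change row uses lesion number and ordinal regression, so this is a simplification.

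**The case against.** The strongest reply is that the plan already uses the baseline scan where it matters. The criterion is about new lesions or an increase, and Table 9 has new-stroke rows and change rows for most features. The baseline readings form part of the outcome in every change row. Nothing says that the absolute rows decide anything; they may simply describe status at one year.

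Most of this stands. A reader might infer that lesions present at entry swamp any drug effect, so that the safety criterion cannot detect harm. The documents do not support that: the new-stroke rows are untouched and the change rows subtract the baseline burden. The loss in the change rows is also smallest where lesions persist most. Nor are the tests invalid: a randomised comparison without baseline adjustment keeps its error rate, as the simulation shows. The issue is precision and chance imbalance.

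Three things remain:

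- The SAP does not say which rows decide the criterion, and protocol 9.2 frames the MRI safety analysis largely as amounts at 12 months.
- Some tested rows have no change counterpart. Microhaemorrhage presence and WMH presence are not among them, since change in number and WMH change cover them.
- CT is allowed at baseline. SAP 26c scores SVD on CT from two features and on MRI from four, so change in SVD score from a CT baseline is not like for like, and no modality term is planned.

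The remedy also has limits. The baseline image is the index-stroke scan, and protocol section 3 sets no maximum time since that stroke. Neither change nor adjustment therefore isolates the treatment year.

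**Conclusion.** The concern holds as one of precision. Every one-year imaging model omits the baseline reading of the same feature, although it has been collected. In the absolute rows the cost is large: variance about 1.3 to 10 times that of an adjusted model for rho 0.5 to 0.95. In the change rows it is about 33% down to 3% over the same range, and close to nil in the microbleed example. The new-stroke rows are unaffected. Because a non-significant result counts as safe, the loss leans one way, but it does not undo the criterion.

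The sizes rest on assumed correlations, prevalences and lesion rates, on about 154 scans per side, and on linear-score approximations to ordinal models. This is a cheap improvement to a secondary outcome of a feasibility trial, not a flaw in its primary endpoint. The diastolic BP gap is minor: 12-month BP is taken in some centres only, and baseline systolic BP is already a covariate.

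**What to change.** In SAP 27b and Table 9:

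1. Add the baseline central reading of the same feature, and baseline modality (CT or MRI), to each absolute and change model for which such a reading exists. Exclude new stroke and index-infarct appearance, which have none.
2. Name the new-lesion rows and the baseline-adjusted models as the analyses that decide the p<0.01 criterion.
3. For microbleeds and the SVD score, either add a not-assessable category for CT-only baselines or state that the analysis is restricted to those with a baseline MRI. Otherwise the complete-case rule in SAP section 20 would silently drop CT-only patients. With a restricted subset the modality term is not needed.
4. In Table 3, add baseline diastolic BP to the diastolic BP model.

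The cost is SAP wording and one or two parameters per model; no new data are needed. CT-baseline patients will add little on microbleeds, and the time between the baseline scan and randomisation remains a limitation to report.
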